The objectives of this study are to clarify: what are the most salient social-ecological risk and resilience factors that should serve as targets for interventions and who are the survivors most at risk to be recruited for future interventions, how survivors want to receive educational interventions, and which educational interventions are most effective. Using a cross-sectional cohort study of 18-25 year old childhood cancer survivors and/or their parents, this study will determine predictors of transition readiness (Aim 1) and predictors of adherence to adult survivor-focused healthcare (Aim 2), as well as evaluate the quality (Aim 3) and efficacy (Aim 4) of electronic educational interventions for AYA survivors. The specific aims are to:

Aim 1: Evaluate social-ecological factors among AYA childhood cancer survivors participating in pediatric survivor care to determine factors associated with decreased transition readiness (i.e., risk factors) and increased transition readiness (i.e., resilience factors), as well as characterize patterns of co-occurring risk factors associated with transition readiness.

Aim 2: Evaluate social-ecological factors among AYA childhood cancer survivors following transfer to identify factors associated non-adherence (i.e., risk factors) and adherence (i.e., resilience factors) to adult survivor care, as well as characterize patterns of co-occurring risk factors associated with non-adherence to adult survivor care.

Aim 3: Develop and assess quality of electronic multimedia materials to educate AYA survivors about lifelong survivor care through qualitative interviews with AYAs.

Aim 4: Evaluate the impact of electronic educational materials on AYA survivors' knowledge about late effects, perceived benefits, self-efficacy, and intentions to engage in lifelong survivor care.

III. Study Design

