This is a mixed methods study involving cohorts of 18-25 year old childhood cancer survivors and/or their parents to determine predictors of transition readiness among those engaged in pediatric survivor care (Aim 1), predictors of adherence to adult survivor-focused healthcare among those who have transferred out of pediatrics (Aim 2), and optimize content, format, and delivery of electronic educational media to increase knowledge about and motivation for survivor care among AYA survivors (Aims 3 & 4). Through our design and methods, we are seeking to clarify what are the most salient social-ecological risk and resilience factors that should serve as targets for interventions, as well as what patterns exist among co-occurring risk factors that maximize patients' risk for poor transition outcomes. The planned approach to accomplish our specific aims will employ both quantitative and qualitative methods to test the following hypotheses:

Aim 1 Hypotheses:

- *A1 Hypothesis 1:* AYA healthcare responsibility, survivor health beliefs, and developmental maturity will be significantly related to increased perceptions of transition readiness.

- *A1 Hypothesis 2:* AYA psychosocial distress, poorer neurocognitive functioning, and deprived neighborhood-level social determinants will be significantly related to decreased perceptions of transition readiness.
- *A1 Hypothesis 3:* The relationship between parental involvement in survivor healthcare and perceptions of transition readiness will be mediated by AYA healthcare responsibility.
- *A1 Hypothesis 4:* When individual transition readiness risk factors are included in principal component analyses (PCA), 2 or more components will emerge indicating subgroups at risk for poor transition outcomes.

Aim 2 Hypotheses:

- *A2 Hypothesis 1:* Survivor health beliefs, developmental maturity, and healthcare responsibility will predict adherence to adult survivor care.
- *A2 Hypothesis 2:* Parental involvement in survivor healthcare will predict adherence to survivor care; this relationship will be stronger for survivors with higher psychosocial distress, as well as lower levels of developmental maturity and neurocognitive functioning.
- *A2 Hypothesis 3:* Access to care problems (e.g., geographical distance, insurance) and lower patient satisfaction will negatively predict adherence to initial survivor care.

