No biological specimens will be collected as part of this research. Participants' electronic medical records will be reviewed to abstract treatment data. Confidentiality within this study will be rigidly maintained. Computer files will use study identification numbers only and are password protected. Only necessary personnel will have access to any of these files. Based on existing best practices for security and privacy in health information technology, we will identify the technologies and features to be employed to ensure privacy and security of personal information. This will address identity and access management, secure storage, secure messaging, encryption, and other security technologies and approaches.

VI. Statistical Analysis Plan

Aims 1 & 2: In 2015, the Aflac Cancer Survivor Program (Aflac CSP) saw over 200 AYA survivors aged 18-22 years (Aim 1). Additionally, the Aflac CSP has transitioned approximately N=165 survivor patients since 2013 (Aim 2). Based on our previous research with survivor patients > 18 years of age, we estimate that less than 2% of AYAs will be non-English speakers. During the year-long study period, we anticipate that there will be at least N=200 AYA patients who are eligible for participation in Aim 1 and at least N=160 AYA patients who are eligible for participation in Aim 2. Previous studies with our AYA population have yielded initial recruitment rates and retention rates above 80%. Of the eligible AYA patients, we estimate that 75% [Aim 1: N=220 patient-parent dyads (440 participants), Aim 2: N=120 patient-parent dyads (240 participants), Aim 3: N= 20 patients, Aim 4: N=58] will participate in each aim of the study. In our univariate analysis, these sample sizes provide us with at least 80% or greater power to detect correlations of magnitude ≥ 0.25 and odds ratios of at least 2.5, depending on the prevalence of the risk factor, assuming that approximately 20-30% of patients meet our definition of successful transition. Power analyses were conducted using PASS v. 11 (Kaysville, UT) using a two-sided test for a single correlation and a two sample Z-test for proportions. Given these anticipated numbers, we can assess at most 15 possible predictors for aim 1 and 12 predictors for aim 2 to ensure that we have at least 10 observations per predictor in our principal component analysis.

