The primary goals of this study are to determine characteristics that influence or predict transition readiness and transition to adult survivor care. Because there are many candidate predictors and overlap between variables with respective substantive meaning, predictors are likely to be highly correlated (i.e., neurocognition and developmental maturity). Therefore, we propose a three-step modeling process to identify general groups or constructs associated with the outcomes of interest. First, in a univariate analysis setting, we will investigate the relationship between each potential predictor and the continuous outcome transition readiness using simple linear regression and correlation analysis. Similarly, we will use Chi-square tests and/or logistic regression to identify factors associated with the binary outcome successful transition (yes/no). Due to the high

correlation/overlap with some of the potential predictors, principal component analysis (PCA) will be performed using those variables significant at the 0.1 level from step 1. The number of components retained in the model will be determined by eigenvalues and percent-variance explained. Finally, based on the results of the PCA, composite variables (which will contain multiple predictors) will be created by standardizing (convert to a z-score) each predictor variable and taking the mean value of the standardized predictor variables that uniquely load on a given component. We will examine the effect of each composite variable on the outcome transition readiness using linear regression and the outcome successful transition using logistic regression. All statistical analyses will be performed using SAS.

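### The Aim 2 power statement is not met as written: for a binary factor among 120 survivors with 20–30% overall success, no prevalence gives 80% power for an odds ratio of 2.5 in a two-sided test at 0.05 or 0.10

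*Combined protocol and SAP*

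**What the plan says.** The power statement is in section VI, Statistical Analysis Plan, Aims 1 & 2. It claims 80% power or more in the univariate analysis for correlations of at least 0.25 and for "odds ratios of at least 2.5, depending on the prevalence of the risk factor, assuming that approximately 20-30% of patients meet our definition"; the outcome meant there is successful transition. The Aim 2 sample is given as "Aim 2: N=120 patient-parent dyads (240 participants"), drawn from "at least N=160 AYA patients who are eligible for participation in Aim 2". The same section reports that "the Aflac CSP has transitioned approximately N=165 survivor patients since 2013". The power software was run "using a two-sided test for a single correlation and a two sample Z-test for proportions".

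No alpha is given for either test. Two levels appear elsewhere in section VI: 0.1, for carrying a variable from the univariate step into the principal component analysis, and 0.05, for the Aim 4 paired t-test. The univariate analysis itself is described thus: "we will use Chi-square tests and/or logistic regression to identify factors associated with the binary outcome successful transition (yes/no"). Section III.A defines the Aim 2 outcome per survivor, as attendance at one or more adult survivorship visits within 18 months of transfer.

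**The concern.** At 20–30% success, 120 survivors yield only 24 to 36 successes. That is few for detecting an odds ratio of 2.5 between two subgroups. The phrase about prevalence suggests that some prevalences achieve 80%; if none does, the qualifier does not save the claim.

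The screening step is where this matters. A factor reaches the principal component analysis and the composite scores only if it passes the 0.10 univariate screen. The aim is to study survivors "following transfer to identify factors associated non-adherence (i.e., risk factors) and adherence (i.e., resilience factors) to adult survivor care", and A2 Hypothesis 3 (section III) states: "Access to care problems (e.g., geographical distance, insurance) and lower patient satisfaction will negatively predict adherence to initial survivor care". Insurance status is naturally a binary factor, and a problem there is expected to lower success. If the stated power is too high, a factor that fails the screen may be read as unimportant when the study had little chance of detecting it.

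**Working it through.** **Inputs.** From section VI: N = 120 survivors, odds ratio (OR) 2.5 or its reciprocal 0.4, overall success π = 0.20 to 0.30, two-sample Z-test. Assumed: two-sided testing; alpha 0.05 (stated only for Aim 4) and, separately, 0.10 (the screening level). Prevalence q is not given, so it was searched from 0.10 to 0.90.

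**Formulas.** The success rates p0 (factor absent) and p1 (factor present) solve

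- p1/(1−p1) = OR × p0/(1−p0)
- (1−q)p0 + q·p1 = π

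With n1 = 120q and n0 = 120 − n1:

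- s0 = √[π(1−π)(1/n0 + 1/n1)], the pooled standard error
- s1 = √[p0(1−p0)/n0 + p1(1−p1)/n1]
- power ≈ Φ[(|p1−p0| − z·s0)/s1], where the opposite tail is negligible

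**One case in full.** Take π = 0.30 and q = 0.40, so n0 = 72 and n1 = 48.

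- p0 = 2/9 = 0.222 and p1 = 5/12 = 0.417. Check: (5/7)/(2/7) = 2.5, and 0.6 × 0.222 + 0.4 × 0.417 = 0.30.
- s0 = √[0.21 × (1/72 + 1/48)] = 0.0854; s1 = 0.0864.
- At 0.05: (0.1944 − 1.960 × 0.0854)/0.0864 = 0.313, so power is 0.623.
- At 0.10: (0.1944 − 1.645 × 0.0854)/0.0864 = 0.625, so power is 0.734.

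**Attempt to reproduce the stated 80%: maximum over prevalence, N = 120, two-sided.** The best prevalence is about 0.37 to 0.43 for OR 2.5. OR 0.4 gives the same maxima at the mirror-image prevalence.

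| Overall success | 0.05, pooled Z | 0.05, exact | 0.10, pooled Z | 0.10, exact |
|---|---|---|---|---|
| 20% | 0.52 | 0.55 | 0.64 | 0.68 |
| 25% | 0.58 | 0.60 | 0.69 | 0.72 |
| 30% | 0.62 | 0.65 | 0.74 | 0.76 |

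The exact columns enumerate both binomials for the uncorrected chi-square (pooled Z) test. An unpooled standard error gives 0.50–0.63 and 0.63–0.74. The stated figure is not reproduced.

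**N needed for 80% at the best prevalence** (20/25/30% success): 240/204/182 at 0.05 and 190/161/144 at 0.10.

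**Chance of failing the 0.10 screen with a true OR of 2.5 or 0.4.** At the best prevalence it is 1 − 0.74 = 26% to 1 − 0.64 = 36%; the stated power implies at most 20%. At 20% prevalence (24 exposed, 96 not) it is 38–44% if the factor raises success, and 52–65% if it lowers success (exact 50–62%).

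**Readings that do reach about 80%** (20/25/30% where three values are shown).

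| Reading | Power | Why the text does not support it |
|---|---|---|
| One-sided 0.10, N = 120 | 0.76/0.81/0.84 | No one-sided test is stated |
| 30% as the reference-group rate, 60/60 split, two-sided 0.10 | 0.79 (exact 0.80) | p1 = 0.75/1.45 = 0.517, so overall success is (0.300 + 0.517)/2 = 41% |
| All 160 eligible survivors, two-sided 0.10 | 0.74/0.80/0.84 | The plan expects 120 |
| 240 patients and parents as independent, two-sided 0.05 | 0.80/0.86/0.90 | There is one outcome per survivor |

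One-sided 0.05 gives the same values as two-sided 0.10, so it also falls short at N = 120.

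**Continuous predictors.** For an OR of 2.5 per standard deviation at N = 120, simulated logistic regression (1,500 fits per success rate, likelihood-ratio test) gives power of about 0.95–0.98 at 0.05 and 0.98–0.99 at 0.10.

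**The case against.** The best defence is that the plan does not state the inputs that would show it to be wrong. It gives no alpha for the Z-test, and its word for sidedness attaches grammatically to the correlation test. A one-sided 0.10 calculation would reach 80% at 25–30% success. This stands in part: the arithmetic is firm only given two-sided testing and 20–30% as an overall rate. A one-sided basis would, however, fit poorly with the planned chi-square test, which is non-directional, and would still fall short at 20% success.

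A second defence is practical. Most Table 2 predictors are questionnaire scales, the study recruits every eligible survivor, and nothing in the conduct of the study would change. That also stands, and it keeps the point modest.

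Three stronger readings are tempting. A reader might infer that parents were counted as independent outcomes, since N = 240 at 0.05 matches the claim across the whole 20–30% range. The documents give the 240 but do not say it was used for power. A reader might infer that Aim 2 is underpowered in general. The shortfall shown here concerns binary factors at an OR of 2.5; scales analysed as continuous at that OR per standard deviation are well covered. A reader might also infer that the sponsor's calculation is proven wrong. What is shown is that the claim cannot be obtained from the stated inputs with a two-sided test at either level found in the plan.

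**Conclusion.** The concern holds for binary factors. With 120 survivors, 20–30% overall success and a two-sided test, maximum power for an OR of 2.5 or 0.4 is 0.52–0.62 at 0.05 and 0.64–0.74 at 0.10, against a stated 80% or more. Exact calculation adds two to four points and does not change the conclusion. The caveat about prevalence does not help, because these are already best-case values. The result rests on two assumptions: that the Z-test was two-sided, and that 20–30% describes all patients, as the sentence says. It should be fixed, as a misstated sensitivity rather than a flaw in design or analysis.

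**What to change.** Restate the Aim 2 part of the sentence with the number of survivors, alpha, sidedness, factor prevalence, direction of effect and the meaning of 20–30%. Use exact figures, because the normal approximation is unreliable when only about one success or fewer is expected among 24 exposed survivors. For example:

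> With 120 survivors, two-sided alpha 0.05 and 30% to 20% overall successful transition, there is 80% power for odds ratios of about 3.1 to 3.8 (or their reciprocals) for a binary factor present in 50% of survivors. For a factor present in 20%, the figures are about 3.7 to 4.0 if it raises success, and only about 1/5.7 (30% success) to 1/12 (20% success) if it lowers success, so power in that last case is very limited.

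If two-sided 0.10 was intended, the exact figures are about 2.7 to 3.2 at 50% prevalence; at 20% prevalence they are 3.2 to 3.5 (raises success) or 1/4.2 to 1/6.6 (lowers success). If a one-sided test, a reference-group rate or a different N was intended, say so, justify it and give the figures for that case. Add that the statement covers binary factors only.

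The cost is a sentence or two of SAP text and a less favourable stated detectable effect. Enrolment and analysis do not change.

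### Aims 1 and 2: step 3 re-tests predictors that step 1 selected on the same outcome in the same participants, so its ordinary p-values are invalid; the composite rule also lacks a sign step

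*Combined protocol and SAP*

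**What the plan says.** Section VI (Statistical Analysis Plan), Aims 1 & 2, introduces the procedure with "The primary goals of this study are to determine characteristics that influence or predict transition readiness and transition to adult survivor care". It has three steps.

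1. Each candidate predictor is related to the outcome one at a time: transition readiness (continuous, Aim 1) or successful transition (yes/no, Aim 2).
2. Then "principal component analysis (PCA) will be performed using those variables significant at the 0.1 level from step 1". Components are retained by eigenvalue and percentage of variance, with no numeric cut-off.
3. Composites of several predictors are built by converting each predictor to a z-score and "taking the mean value of the standardized predictor variables that uniquely load on a given component". Then "We will examine the effect of each composite variable on the outcome transition readiness using linear regression", with logistic regression for successful transition.

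On size, the section says "we can assess at most 15 possible predictors for aim 1 and 12 predictors for aim 2", so as to have "at least 10 observations per predictor in our principal component analysis". It claims "at least 80% or greater power to detect correlations of magnitude" 0.25 or more in the univariate step.

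For Aims 1 and 2 the documents give no step-3 significance level, sample split, cross-validation, permutation, correction for selection or multiplicity rule. They do not say that scales are coded in one direction or that negative loadings are reversed, and step 3 is not labelled exploratory.

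**The concern.** There are two faults in the same step.

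**Selection.** Every predictor in a step-3 composite is there because it correlated with the outcome in this sample. Testing the composite against the same outcome uses the same chance association twice. The usual p-value assumes that the composite was chosen without looking at the outcome.

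**Signs.** Every variable that passes step 1 enters the PCA, so scales pointing in opposite directions can fall on one component. Table 2 (Section III.D) lists anxiety, depression, anger, social isolation and post-traumatic stress in the same row as self-esteem, peer relationships and post-traumatic growth. A plain mean of such scales partly cancels.

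The Background says that the study will show which factors to target, for use in later intervention grants. A composite of unrelated predictors that passed the screen cannot be told from a real weak one in ordinary output, and a real construct measured by opposed scales may be missed.

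**Working it through.** **The plan's own figure.** Power for one correlation, two-sided 0.05 (assumed), is Φ(atanh(r)·√(N−3) − 1.96). With r = 0.25 and N = 120: 0.2554 × 10.817 − 1.96 = 0.803, power 0.789. With N = 220: 0.2554 × 14.731 − 1.96 = 1.802, power 0.964. The stated 80% is essentially reproduced for step 1. It says nothing about step 3.

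**Why the step-3 p-value fails.** With no true association, each predictor passes the screen with probability 0.10. At least one of 15 independent predictors passes in 1 − 0.9^15 = 79% of studies, and at least one of 12 in 1 − 0.9^12 = 72%. For a single predictor that has passed, the chance of p<0.05 is already 0.05/0.10 = 50%. Averaging k predictors that each correlate r with the outcome and ρ with each other gives composite r = k·r/√(k + k(k−1)ρ). For k = 3 and ρ = 0.5 this is 3r/√6 = 1.225r. At N = 120 the p<0.1 threshold is |r| = 0.151 and the p<0.05 threshold is 0.179. Three same-direction predictors that only just pass give 1.225 × 0.151 = 0.185, which is significant automatically. The same holds at N = 150 (0.165 against 0.160) and N = 220 (0.136 against 0.132).

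**Simulation of the written pipeline.** From the plan: the p<0.1 screen, the mean of z-scores, N = 120 (Aim 2), and for Aim 1 both N = 220 (stated) and N = 150 (75% of 200 eligible). Assumed, because the plan is silent: blocks of three scales with within-block |r| 0.5, eigenvalue >1, varimax, each variable assigned to its largest loading, step-3 level 0.05. Only multi-predictor composites count. The cap of 15 or 12 is tied to the PCA, so step 1 was run with 12 or 15 candidates and also with 45 (Table 2 names about 42–48 by my count).

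No true association:

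| | Mixed directions, as written | Same direction | Signs aligned, screen kept | No screen |
|---|---|---|---|---|
| p<0.05 per tested composite | 36–38% | 63–72% | 75–80% | about 5% |
| Any false positive, 12 or 15 candidates | 13–18% | 25–31% | 27–33% | 17–24% |
| Any false positive, 45 candidates | 52–53% | 70–73% | 78–82% | 51–56% |

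The first row applies when a composite forms. With 12 or 15 candidates, 56–67% of null studies form none; with 45, 7–9%. A separately coded run with a stricter loading rule (at least 0.4 on one component only) gave 38–41% as written and 80–90% aligned. A binary outcome with 25% successes at N = 120 (correlation test in place of logistic regression) gave 36–38%, 63–72% and 78–81%.

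One real construct (composite r 0.25): at least one composite made only of unrelated predictors reached p<0.05 in 8–15% of studies as written and 19–27% signed with 12 or 15 candidates, and in 46–48% and 71–78% with 45. A separate run with 12 or 15 candidates supplies the unscreened comparison: 8–15% screened against 16–21% unscreened as written, and 16–25% against 12–19% signed.

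Size and coverage (N = 120–220, same direction or signed):

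| Population composite r | Mean reported r | Coverage of ordinary 95% interval |
|---|---|---|
| 0.09 | 0.17–0.24 | 58–81% |
| 0.15 | 0.19–0.26 | 84–94% |
| 0.20 | 0.22–0.28 | 92–96% |
| 0.25 | 0.26–0.29 | 95–97% |
| 0.30 | 0.30–0.32 | 95–98% |
| 0.35 | 0.35–0.36 | 94–97% |

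For composites of unrelated predictors only, coverage is 13–36%.

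**Signs.** For k scales with intercorrelation |r| and net = scales one way minus scales the other, the composite's correlation with its construct is √r·net/√(r·net² + (1−r)k). Five distress and two positive scales at r = 0.5: unsigned (net 3) 0.7071 × 3/√(4.5 + 3.5) = 0.75; signed (net 7) 0.7071 × 7/√(24.5 + 3.5) = 0.94. At r = 0.3 the pair is 0.60 and 0.87; at r = 0.7 it is 0.87 and 0.97. Through all three steps, a construct with true r 0.30 is reported on average as 0.23–0.24 unsigned and 0.29–0.31 signed.

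**The case against.** The best defence is that no stated hypothesis depends on a step-3 p-value. The hypotheses on individual factors can be addressed outside step 3, and Hypothesis 4 for each aim asks only whether two or more components emerge. Section VI only says that it will examine the effect of composites, sets no step-3 level, and feeds later grant applications in which a false lead would be tested again. That ordinary p-values will be reported is an inference. It is a fair one, since regression is named, no alternative is given, and the aim is described as a primary goal.

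The high rates are also conditional on a composite forming. With mixed directions as written, the screen adds nothing to the study-wide error, and much of that error is ordinary multiplicity. This stands. The 45-candidate results rest on reading the cap as applying to the PCA only. Effects at the plan's target of 0.25 are little distorted. All of this limits the harm to absent and weak associations; it does not make the p-values valid.

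Hypothesis 4 calls the PCA inputs risk factors, which may imply that scales will be coded in the risk direction, and sharing a table row does not prove that scales share a component. One clause would settle it.

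Finally, a global permutation test does not by itself say which construct matters, and scoring zero when no composite forms ignores a strong lone predictor. Both limits are real.

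**Conclusion.** The concern holds and should be fixed. Followed as written, step 3 gives p-values that cannot be taken at face value: 36–72% of multi-predictor null composites reach p<0.05, depending on scale direction, instead of about 5%. Ordinary intervals fail for absent or weak associations; those at r 0.25 or above are little affected. Study-wide, the excess over an unscreened analysis is nil with mixed directions and clear with one direction. The missing sign step weakens a real construct measured by opposed scales (0.75 against 0.94 in the example).

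The exact rates depend on the assumed block structure, loading rule and 0.05 level. Within-block |r| of 0.3 and 0.7 at N = 150 gave 36–39% (mixed, as written) and 56–73% (same direction), so the conclusion does not turn on one choice. The two faults must be repaired together: aligning signs while keeping the screen raises the per-composite rate to 75–80%.

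**What to change.** In Section VI, Aims 1 & 2:

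- **Sign step.** State that each z-score is multiplied by the sign of its loading before averaging.
- **Valid test.** Keep the screen, which fits Hypothesis 4, but permute the outcome and repeat all three steps in each permutation. Take the largest absolute composite correlation as the statistic (zero if no composite forms) and report one p-value per outcome. In simulation this rejected in 4.6–5.8% of null studies with 12, 15 or 45 candidates, including a 25% binary outcome.
- **Reporting.** Present individual step-3 coefficients as descriptive, without ordinary p-values, and note that weak effects are inflated. Each composite may be compared with the same maximum reference to show where the signal lies. With one real construct, a composite of unrelated predictors was flagged in 2–4% of studies; this is a simulation result, not a proof of control.

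If a formal test per composite is wanted, run the PCA on a prespecified list of at most 15 (Aim 1) or 12 (Aim 2) predictors without the outcome screen, with the sign step and Holm across composites (4–6% any false positive).

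**Cost.** A few sentences, a short program, and one formal test per outcome instead of one per composite. No new data are needed. Power of the permutation test for one three-scale construct, with the Holm option alongside:

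| | N=120 | N=150 | N=220 |
|---|---|---|---|
| Permutation, r 0.25, 12 or 15 candidates | 47% | 54% | 76% |
| Permutation, r 0.25, 45 candidates | 28% | 38% | 57% |
| Permutation, r 0.35, 12 or 15 candidates | 85% | 92% | 99% |
| Permutation, r 0.35, 45 candidates | 70% | 82% | 95% |
| Holm option, r 0.25 | 61–64% | 72% | 88–90% |

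The sign step recovers some power. For a construct with r 0.30 on five plus two opposed scales, the permutation test has 72%, 78% and 93% power signed, against 44%, 48% and 72% unsigned. The Holm option's price is that its list must be chosen in advance from about 42–48 variables and no longer follows from identified risk factors as Hypothesis 4 describes.
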